7.3.3. Subgroup Analyses

Subgroup analyses of primary efficacy endpoint will be performed to determine whether treatment effects are consistent across clinically important subgroups. Testosterone castration rates at Week 49 Day 1 (Day 337) for relugolix arm and their 95% CI will be displayed in a forest plot. Similarly, the difference in testosterone castration rates at Week 49 Day 1 between relugolix and leuprolide arms and their 95% CI will also be displayed in a forest plot. Subgroups will include but not be limited to the following:

- Geographic region (North and South America, Europe, Asia and Rest of World);
- Geographic region (North America, other regions);
- Geographic region (Asia [Japan, Korea, China, and Taiwan], other regions);
- Ethnicity (Hispanic or Latino, Not Hispanic or Latino);
- Presence of metastatic disease (yes, no) per IWRS;
- Presence of metastatic disease (yes, no) per CRF if > 5% discrepancy from IWRS;
- Age category (≤ 75 years old, > 75 years old);
- Race (white, Black/African American, Asian, or others);
- Clinical disease state presentations (biomedical or clinical relapse, newly diagnosed metastatic disease, advanced localized disease);
- Gleason score at study entry (< 8 , ≥ 8);
- Baseline testosterone level (< 250 ng/dL, ≥ 250 ng/dL);
- Baseline PSA level (< 20 ng/mL, ≥ 20 ng/mL).

In addition, testosterone castration rates at Week 49 Day 1 (Day 337) for the two different dose levels (22.5 mg vs. 11.25 mg) in leuprolide arm and their 95% CI will be provided separately.

7.4. Secondary Efficacy Endpoints

7.4.1. Key Secondary Efficacy Endpoints with Alpha-Protection

The key secondary endpoints will be tested in the following order (see [Figure 2](#)) for different regulatory agencies, with a fixed-sequence testing procedure to control the overall familywise error rate at a two-sided type I error rate of 0.05 across primary and key secondary endpoints.

[figure not shown]
For the testing order to be submitted to the FDA, Evaluation Criterion 2 for noninferiority of the primary efficacy endpoint will be assessed first in the order of hierarchical hypothesis testing for the key secondary endpoints after Evaluation Criterion 1 is met.

For the testing order to be submitted to EMA and PMDA, Evaluation Criterion 2 for noninferiority of the primary efficacy endpoint will be the primary efficacy assessment.

Timing of analyses for primary and key secondary endpoints is also included in [Table 4](#).

Castration resistance free survival and time to testosterone recovery back to 280 ng/dL at 90-day follow-up will be tested at the final analysis only if all the above endpoints reach statistical significance in the primary analysis. Endpoints in the higher order will be updated with descriptive statistics in the final analysis.

Figure 2: Diagram of Testing Order in Primary and Key Secondary Endpoints for Different Regulatory Agencies

Abbreviations: CI = confidence interval; EMA = European Medicines Agency; PC = prostate cancer; US FDA = United States Food and Drug Administration; PMDA = Japanese Pharmaceutical and Medical Device Agency.

Table 4: Testing Order and Timing of Analysis for Primary and Key Secondary Endpoints for Different Regulatory Agencies

Endpoints	Testing Order for the US FDA		Testing Order for EMA and PMDA	
	At Primary Analysis	At Final Analysis	At Primary Analysis	At Final Analysis
Sustained castration rate per Evaluation Criterion 1 ($\geq 90\%$ in relugolix)	1	Update	NA	Update
Sustained castration rate per Evaluation Criterion 2 (noninferiority of relugolix compared with leuprolide acetate)	2	Update	1	Update
Castration rate on Week 1 Day 4	3	Update	2	Update
Castration rate on Week 3 Day 1	4	Update	3	Update
Confirmed PSA response rate at Week 3 Day 1	5	Update	4	Update
Profound castration rate at Week 3 Day 1	6	Update	5	Update
FSH level at Week 25 Day 1	7	Update	6	Update
Castration resistance free survival during the 48-week treatment in patients with metastatic prostate cancer ^a	NA	8	NA	7
Castration resistance free survival during the 48-week treatment in patients with or without metastatic prostate cancer ^a	NA	9	NA	8
Time to testosterone recovery back to 280 ng/dL at the 90-day follow-up in patients participating in testosterone recovery follow-up ^a	10 ^b	NA	9 ^b	NA

Abbreviations: EMA = European Medicines Agency; FSA = follicle-stimulating hormone; NA = not applicable; PSA = prostate-specific antigen; US FDA = United States Food and Drug Administration.

^a Castration resistance free survival and time to testosterone recovery back to 280 ng/dL at the 90-day follow-up will be tested at the final analysis only if all the above endpoints reach statistical significance in the primary analysis. Endpoints in the higher order will be updated with descriptive statistics in the final analysis.

^b Analysis of time to testosterone recovery back to 280 ng/dL at the 90-day follow-up will be performed at the primary analysis. Testing order of time to testosterone recovery will be followed by castration resistance free survival in the final analysis.

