7.2. Multiplicity Adjustment

The primary and the key secondary efficacy analyses will be performed at an overall two-sided type I error of 0.05. A test will be deemed statistically significant if the two-sided p-value rounded to 4 decimal places is less than 0.05. If the result of the primary endpoint analysis meets the respective evaluation criterion of the primary endpoint, the key secondary endpoints will then be tested with a fixed-sequence testing procedure (as illustrated in [Figure 2](#)) to maintain the overall familywise error rate of 0.05 for the testing of primary and key secondary endpoints.

The key secondary endpoints with alpha protection for labelling purposes are identified and defined in [Section 7.4.1](#).

All p-values (if provided) aside from the endpoints listed in the testing order are not adjusted in multiplicity, thus are at a nominal level of 0.05.

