7.4.3.5. Time to Testosterone Recovery

Testosterone levels will be followed for up to 90 days in approximately 100 patients randomized to relugolix and approximately 50 patients randomized to leuprolide acetate who complete 48 weeks of treatment and who do not plan to start alternative androgen deprivation therapy within the following 12 weeks (or within 24 weeks following the last injection of leuprolide acetate). As the enrollment for the follow-up of testosterone recovery has been completed for the patients enrolled under protocol amendment 2, analysis of time to testosterone recovery will be performed in the primary analysis and there will be no updates in the final analysis.

Patients will be censored at the time of last follow-up visit or initiation of treatments known to suppress testosterone (refer to [Appendix Table 1](#)), whichever comes earlier.

Time to testosterone recovery will be summarized using the Kaplan-Meier method with the following 3 testosterone recovery levels:

- ≥ 50 ng/dL (1.7 nmol/L);
- Above baseline level or 280 ng/dL;
- Above 280 ng/dL (as one of the key secondary endpoints).

Cumulative incidence of time to testosterone recovery at the 30-day, 60-day and 90-day follow-up visits will be estimated by treatment group along with 95% CI.

The unstratified test via log-log transformation of the difference in cumulative incidence of time to testosterone recovery back to 280 ng/dL will be compared at the 90-day follow-up visit (unstratified test version as in Section 7.4.3.1).

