7.4.3.7. Castration Resistance Free Survival

Castration resistance free survival will not be analyzed for the primary analyses but will be analyzed at the final analyses when approximately 390 patients with metastatic disease have been randomized to the study and have had the opportunity to be evaluated for 48 weeks of study treatment and completed the 30-day safety follow-up or discontinued early.

Castration resistance free survival is in the key secondary endpoints and will be analyzed under metastatic patients only and mITT population. PSA results and deaths from follow-up visits will be excluded from the analysis. Patients with metastatic disease will be identified through presence of distant metastasis (M1) at study entry reported in the CRF. If the discrepancy between IWRS and CRF is $> 5\%$, sensitivity analysis based on the presence of metastatic disease reported in the IWRS will be performed.

Castration resistance free survival is defined as the time from the date of first dose to the date of PSA progression while castrated or death due to any reason, whichever occurs earlier. A confirmed PSA progression prior to testosterone escape or the date of testosterone censoring will be considered as an event. Patients will be censored at the last PSA assessment prior to follow-up visits, the date of censoring for testosterone, or the date of testosterone escape, whichever comes earlier.

As a sensitivity analysis, patients will be censored at the last available assessment prior to the follow-up visits, the date of censoring for testosterone, the date of testosterone escape, or the time of initiating androgen receptor inhibitors (eg, enzalutamide), whichever comes earlier.

Castration resistance free survival will be analyzed using the Kaplan-Meier method. Treatment comparison with hazard ratio will be performed using Cox proportional hazard model and p-value will be provided using unstratified log-rank test on patients with metastatic disease and stratified log-rank test on mITT population. Proportionality in survival curves between two treatment groups will be assessed. CRFS rate at Week 49 Day 1 (Day 337) will be estimated along with 95% CI.

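### The SAP gives the testosterone-recovery test two timings and two places in the fixed sequence, so 5% familywise error is not guaranteed for the last three key secondary tests

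*SAP*

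**What the plan says.** Section 7.4.1 says the key secondary endpoints are tested "with a fixed-sequence testing procedure to control the overall familywise error rate at a two-sided type I error rate of 0.05", across the primary and key secondary endpoints. Section 7.2 sets the level of each test: "A test will be deemed statistically significant if the two-sided p-value rounded to 4 decimal places is less than 0.05".

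On the timing of the recovery test (280 ng/dL at the 90-day follow-up) there are two statements:

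- Final analysis. Section 7.4.1 and footnote a to Table 4 say that CRFS and recovery "will be tested at the final analysis only if all the above endpoints reach statistical significance in the primary analysis".
- Primary analysis. Footnote b says "Analysis of time to testosterone recovery back to 280 ng/dL at the 90-day follow-up will be performed at the primary analysis". Section 7.4.3.5 says "analysis of time to testosterone recovery will be performed in the primary analysis and there will be no updates in the final analysis". Table 4 agrees: recovery's rank stands in the primary-analysis column, with NA at the final analysis.

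On the order there are also two statements:

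- After CRFS. Table 4 ranks metastatic CRFS 8 (FDA) or 7 (EMA and PMDA), all-patient CRFS 9 or 8, and recovery 10 or 9.
- Before CRFS. The second sentence of footnote b reads "Testing order of time to testosterone recovery will be followed by castration resistance free survival in the final analysis".

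The timing of CRFS is not in doubt. Section 7.4.3.7 says "Castration resistance free survival will not be analyzed for the primary analyses but will be analyzed at the final analyses".

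**The concern.** A fixed sequence controls the familywise error because each hypothesis is tested only after every hypothesis ahead of it has been rejected. That needs one order, fixed in advance, and a gate that follows it.

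Here the lowest-ranked test is scheduled before the two tests ranked above it can exist. The written gate does not repair this. It asks only for significance at the primary analysis, when CRFS is not tested. No sentence says that recovery's confirmatory conclusion waits for CRFS, that CRFS depends on recovery, or that all-patient CRFS depends on metastatic CRFS.

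Two questions therefore have no single answer in the SAP: whether a recovery claim made at the primary analysis survives a failed CRFS test, and whether CRFS may be tested after recovery has failed. Section 7.2 describes these endpoints as alpha-protected for labelling, so the answers decide which claims stand. The recovery result will also be known before CRFS is tested, so an order settled at that point would depend on the data.

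**Working it through.** **Inputs.** Level of each test: two-sided 0.05 (Section 7.2). Claimed familywise error: 0.05 (Section 7.4.1). Ranks and timings: Table 4 and its footnotes. Planned CRFS events: about 107 in metastatic patients and about 149 in all patients (Section 2.2).

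The SAP gives no correlations between the tests, so these are assumptions. Recovery with CRFS: 0, 0.3 and 0.5. The two CRFS tests with each other: 0.6, and about 0.85. The latter comes from treating the metastatic events as nested in the total: √(107/149) = 0.847.

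All results assume that every endpoint through FSH has passed and that the remaining nulls are true. Correlated cases come from 2,000,000 simulated draws.

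**Step 1: the SAP's own figure.** In a strict chain with all remaining nulls true, an error requires the first test in the chain to reject. The familywise error is then the level of that first test, 0.05. This holds for metastatic CRFS, then all-patient CRFS, then recovery. It holds equally for recovery first and CRFS after. The claimed 5% is reproduced under either order.

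**Step 2: recovery claimed at the primary analysis, metastatic CRFS tested later whatever recovery showed.** The error is the probability that either test rejects.

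- Independent: 1 − 0.95² = 0.0975.
- Correlation 0.3: about 0.095.
- Correlation 0.5: about 0.091.
- Upper bound: 0.05 + 0.05 = 0.10.

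Choosing the order after seeing the recovery p-value gives the same result. If recovery is significant it is put first and claimed; if not, CRFS is put first and tested at 0.05.

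**Step 3: the gate of Section 7.4.1 and footnote a taken alone, with all three tests conditional only on primary-analysis endpoints.**

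- Independent: 1 − 0.95³ = 0.1426.
- Assumed correlations: from 0.133 (recovery–CRFS 0, CRFS–CRFS 0.6) down to 0.112 (0.5 and about 0.85).
- Upper bound: 3 × 0.05 = 0.15.

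| Reading | Familywise error | Bound |
|---|---|---|
| Table 4 ranks, recovery claim waits for both CRFS tests | 0.05 | 0.05 |
| Recovery first, CRFS gated on it | 0.05 | 0.05 |
| Recovery and metastatic CRFS do not gate each other | 0.091 to 0.0975 | 0.10 |
| All three gated only on primary-analysis endpoints | 0.112 to 0.1426 | 0.15 |

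**The case against.** The best defence is that the SAP is clumsy, not unsound. Sections 7.2 and 7.4.1 both prescribe a fixed sequence, Table 4 numbers the tests, and Table 1 also lists recovery after both CRFS endpoints. A largely coherent reading follows: recovery is computed once on primary-analysis data and not updated, and takes its formal place after CRFS at the final analysis. The second sentence of footnote b may then be bad grammar for the statement that recovery follows CRFS. Computing a result early spends no alpha if the claim waits. Figure 2, to which the SAP refers for the order, is not shown in the copy reviewed and may settle it.

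Much of this stands. A reader might infer from the conflicting passages that the sequence fails to control the familywise error, or that the trial's error is 9.75%. The document supports neither. Either single order gives 5%, inflation needs a reading in which the tests do not gate each other, and 9.75% is a two-test figure under assumed independence.

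The defence does not remove the problem. The SAP nowhere says that the recovery claim waits. The coherent reading has to set aside a sentence of footnote b, and it leaves recovery's rank in the primary-analysis column, with NA at the final analysis, unexplained. A figure could show the intended order, but the conflicting sentences would still be in the text.

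**Conclusion.** The point holds in a limited form. The timing and the order of the recovery test are each stated in two incompatible ways, and the gate as worded cannot enforce the Table 4 ranks. The 5% familywise error is therefore not guaranteed as written for metastatic CRFS, all-patient CRFS and recovery.

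The size depends on the reading: 5% under either strict order, about 9.1% to 9.75% if recovery and metastatic CRFS do not gate each other, and about 11% to 14.3% if all three are gated only on primary-analysis endpoints. These figures are conditional on the earlier endpoints having passed, on the remaining nulls being true and on the assumed correlations. Only the bounds of 10% and 15% are free of the correlation assumption.

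Evaluation Criteria 1 and 2 and the key secondary endpoints through FSH are untouched. It still needs correcting, because the conflict decides which alpha-protected claims stand.

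**What to change.** Amend the SAP wording before the primary-analysis database lock, and so before the recovery result is known:

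1. State one order in Section 7.4.1, Table 4 and footnotes a and b, keeping the Table 4 ranks: metastatic CRFS, then all-patient CRFS, then recovery. Check that Figure 2 agrees.
2. State that recovery is computed once, on primary-analysis data, and is declared significant only after both CRFS tests succeed at the final analysis. Until then its p-value is nominal.
3. Delete or correct the second sentence of footnote b.
4. Replace the gate with one that requires significance of all higher-ranked endpoints, at whichever analysis each is tested. This also makes all-patient CRFS conditional on metastatic CRFS.

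No design change or new data are needed. The cost is that the formal recovery claim waits for the final analysis and depends on both CRFS tests. If each has its stated power of about 85%, both succeed with probability between 0.85 × 0.85 = 0.7225 (independent) and 0.85 (fully dependent). The Table 4 ranks already imply that dependence.

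Putting recovery first would also give 5%, but it is not recommended as a wording repair. It would make the CRFS tests, which have a stated power calculation, conditional on a subset of about 150 patients for which the SAP states none.

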7.4.2. Other Secondary Efficacy Endpoints

Other secondary efficacy endpoints include the following:

- Sustained profound castration rate from Week 5 Day 1 through Week 49 Day 1 defined as the cumulative probability of testosterone suppression to < 20 ng/dL (0.7 nmol/L) while on study treatment from Week 5 Day 1 through Week 49 Day 1;
- Sustained profound castration rate from Week 25 Day 1 through Week 49 Day 1 defined as the cumulative probability of testosterone suppression to < 20 ng/dL (0.7 nmol/L) while on study treatment from Week 25 Day 1 through Week 49 Day 1;
- Profound castration rate at Week 1 Day 4;
- Time to testosterone recovery back to > 50 ng/dL;
- Time to testosterone recovery back to > 280 ng/dL or baseline;
- PSA response rate at Week 3 Day 1 and Week 5 Day 1;
- Proportion of patients with PSA concentration < 0.02 ng/mL (0.02 μ g/L) at Week 25 Day 1 visit;
- Time to PSA progression;
- FSH level over time (analysis details refer to [Section 8](#)).
- Absolute values and changes from baseline in the scores of each domain in EORTC-QLQ-C30 and EORTC-QLQ-PR25, at regular intervals during treatment, and during the Follow-Up and/or End of Treatment visits (analysis details refer to [Section 7.6](#)).

7.4.3. Analyses of Secondary Efficacy Endpoints

7.4.3.1. Castration Rate and Profound Castration Rate at Day 4 and Week 3 Day 1

Castration rate at Day 4 and Week 3 Day 1 (ie. Day 15) are in the key secondary endpoints and will be estimated by use of the Kaplan-Meier method based on time to first testosterone castration, which is defined as time from the date of first dose to the date of initial testosterone suppression to < 50 ng/dL (1.7 nmol/L).

The Kaplan-Meier method will be applied with the following,

- Patients with initial testosterone suppression to < 50 ng/dL (1.7 nmol/L) will be considered as an event at the time of initial suppression.
- Patients without testosterone suppression to < 50 ng/dL (1.7 nmol/L) will be censored at the last available assessment prior to the follow-up visits.

Cumulative incidence curve of time to first testosterone castration will be plotted and summarized by treatment group. Castration rates at Day 4 and Week 3 Day 1 based on the cumulative incidence curve of time to first testosterone castration will be estimated along with 95% CI.

Treatment difference in castration rates at Day 4 and Week 3 Day 1 between relugolix and leuprolide acetate will be estimated along with 95% CI using a similar method to that described

in [Section 7.3.1](#). The stratified test statistics via log-log transformation of the difference in cumulative incidence curve at a fixed time point is constructed by ([Klein 2007](#)).

$$x^2 = \frac{\left\{ \sum_{s=1}^M \log \left(-\log \left(\widehat{S}_{R_s}(t) \right) \right) - \log \left(-\log \left(\widehat{S}_{L_s}(t) \right) \right) \right\}^2}{\sum_{s=1}^M \left\{ \frac{V(\widehat{S}_{R_s}(t))}{\left[\widehat{S}_{R_s}(t) \log \left(\widehat{S}_{R_s}(t) \right) \right]^2} + \frac{V(\widehat{S}_{L_s}(t))}{\left[\widehat{S}_{L_s}(t) \log \left(\widehat{S}_{L_s}(t) \right) \right]^2} \right\}}$$

Where s is the s^{th} stratum in the total of M strata and $t = \text{Day 4 and Week 3 Day 1}$ in this case. Each stratified test statistics at a fixed time under two samples follows a chi-square distribution with one-degree freedom. If the stratified test statistics cannot be calculated due to event having not occurred in certain stratum, unstratified test will be used instead. If unstratified test is still not estimable, the stratified version of the Mantel-Haenszel test using pooled Kaplan-Meier estimators in each stratum will be constructed as the following. This test statistics follows a chi-square distribution with one-degree freedom.

$$\chi_{MH}^2 = \frac{\left\{ \sum_{s=1}^M \frac{n_{R_s} n_{L_s}}{n_{R_s} + n_{L_s}} \left(\widehat{S}_{R_s}(t) - \widehat{S}_{L_s}(t) \right) \right\}^2}{\sum_{s=1}^M n_{R_s} n_{L_s} V(\widehat{S}_{pooled_s}(t))}$$

Profound castration rate at Day 4 and Week 3 Day 1 will be analyzed similarly as above with $< 20 \text{ ng/dL}$ (0.7 nmol/L) as testosterone suppression criterion. Profound castration rate at Week 3 Day 1 is one of the key secondary endpoints and will be compared between relugolix and leuprolide acetate using the stratified test statistics, as above.

Testosterone level and percentage change from baseline in testosterone level at each visit will be summarized by treatment group. Categorical summary of testosterone level in the first 4 weeks of treatment will be also summarized. Due to the different visit schedule in the original protocol versus protocol amendment 2, testosterone level in the first 4 weeks under the original protocol will be summarized additionally using the visit windows in [Table 5](#). The same rule in [Section 4.3.6](#) for handling multiple assessments in one visit will be used.

Table 5: Visit Windows in the First 4 Weeks under Original Protocol

Visit	Start Day	Target Day	End Day
Week 1 Day 4 ^a	1	4	5
Week 2 Day 1	6	8	11
Week 3 Day 1	12	15	18
Week 4 Day 1	19	22	25
Week 5 Day1	26	29	43

^a Start day of Week 1 Day 4 only includes postbaseline assessments on or after the first dose.

7.4.3.2. Sustained Profound Castration Rate

Sustained profound castration rates are defined for two treatment periods:

- Sustained profound castration rate from Week 5 Day 1 through Week 49 Day 1 is defined as the cumulative probability of testosterone suppression to < 20 ng/dL (0.7 nmol/L) while on treatment from Week 5 Day 1 through Week 49 Day 1;
- Sustained profound castration rate from Week 25 Day 1 through Week 49 Day 1 is defined as the cumulative probability of testosterone suppression to < 20 ng/dL (0.7 nmol/L) while on treatment from Week 25 Day 1 through Week 49 Day 1.

The Kaplan-Meier method described in Section 7.3.1.2 will be applied similarly by changing the castration level (< 50 ng/dL) to profound castration level (< 20 ng/dL). Sustained profound castration rate from Week 25 Day 1 through Week 49 Day 1 is described below.

Definition of Testosterone Test Result at Week 25 Day 1

Serum concentration of testosterone at Week 25 Day 1 can be obtained at Day 169 with a visit window from Day 156 to Day 183 inclusive. If more than one test result lies within the visit window, the result with the closest study day to Day 169 will be used as testosterone test result at Week 25 Day 1. If there are two results equidistant to the scheduled target day, the earlier assessment will be used as testosterone test result at Week 25 Day 1.

Kaplan-Meier Analysis

Any testosterone test result rising above the profound castration level (≥ 20 ng/dL) between Week 25 Day 1 and Week 49 Day 1 will be considered as an event in the Kaplan-Meier analysis.

Patients who have not reached profound castration level at Week 25 Day 1 will be considered as having had an event at the target day of Week 25 Day 1.

Patients who discontinued from the study prior to Week 25 Day 1 will be censored at the target day of Week 25 Day 1. In addition, patients without a Week 25 Day 1 assessment will be considered to have had an event at the target day of Week 25 Day 1.

For patients reaching profound castration levels at Week 25 Day 1, the following rules will be applied to the Kaplan-Meier analysis for estimation of sustained profound castration rate with consideration for missed visits. Time to event or censoring, whichever occurs first, will be used in Kaplan-Meier analysis.

- a) Patients who had one or more consecutive missed visits (ie, a visit gap of > 42 days) and had a non-profound castrated assessment immediately after the missed visit(s) will be considered as having an escape at the target day of the earliest missed visit prior to the non-profound castrated assessment;
- b) Patients with one missed visit who has a profound castrated assessment immediately before and after the missed visit will be assumed to be profound castrated at the missed visit;
- c) Patients with two or more consecutive missed visits (ie, a visit gap of > 70 days) and who had a profound castrated assessment immediately before and after the missed visits will be censored at the last available testosterone assessment prior to the missed visits.

7.4.3.3. Prostate-Specific Antigen Response Rate at Week 3 Day 1 and Week 5 Day 1

Proportion of patients with PSA reduction from baseline at Week 3 Day 1 and Week 5 Day 1 will be summarized along with 95% exact CI. Patients without PSA assessment at Week 3 Day 1 and Week 5 Day 1 will be considered as nonresponders. The following two criteria will be considered for PSA reduction:

- > 50% reduction from baseline;
- > 90% reduction from baseline.

Confirmed PSA response at Week 3 Day 1 is one of the key secondary endpoints and defined as > 50% reduction in PSA from baseline at Week 3 Day 1 followed with confirmation at Week 5 Day 1. Treatment comparison between relugolix and leuprolide acetate will be performed using a stratified Cochran-Mantel-Haenszel test.

Change from baseline in PSA at Week 3 Day 1 and Week 5 Day 1 will be also summarized.

7.4.3.4. Undetectable Prostate-Specific Antigen Rate at Week 25 Day 1

Proportion of patients who have a PSA concentration < 0.02 ng/mL (0.02 µg/L) at Week 25 Day 1 will be summarized by treatment group along with 95% exact CI. Patients with missing PSA assessment at Week 25 Day 1 will be considered as nonresponders.

